In Phase 1 of the study, two other clinical decision rules were derived retrospectively. By analyzing the characteristics of patients who had an anaphylactic reaction, we were able to derive a rule to identify a low-risk group of biphasic reaction (any symptom of allergy) and clinically significant biphasic reaction (i.e. meeting the criteria for an anaphylactic reaction). These rules were created with the highest possible negative predictive sensitivities and values (VPNs).

The next step is to prospectively verify whether these rules maintain their sensitivity and negative predictive value with a different sample of patients from the same population pool. The first rule assesses the probability of clinically significant biphasic reactions (sensitivity of 90%, 7 variables; Table 3) and the second, all biphasic reactions (100%, 7 variable sensitivity; Table 4). Areas below the ROC curve were 0.896 and 0.874, respectively. Because the variables selected for each decision-making rule come from a regression model, the predicted probability of a biphasic reaction comes from the linear combination of selected variables. Depending on the coefficients calculated, each variable present in the patient will have a different weight in the decision.

TABLE 3: RETROSPECTIVELY DERIVED CLINICAL DECISION RULE FOR CLINICALLY SIGNIFICANT BIPHASIC REACTIONS

| | |
|----|--|
| 1. | ATCD allergy to a different agent than the one in question |
| 2. | Symptoms of diarrhea |
| 3. | ATCD allergy to the same agent as the one in question |
| 4. | Number of doses of O.R. in the emergency room |
| 5. | Food allergen (other than milk, egg, peanuts, seafood) |
| 6. | Number of doses of O.R. before emergency 1 |
| 7. | ENT symptoms |

TABLE 4: RETROSPECTIVELY DERIVED CLINICAL DECISION RULE FOR BIPHASIC REACTIONS (ALL SEVERITIES CONFUSED)

| | |
|----|---|
| 1. | Number of doses of O.R. in the emergency room |
| 2. | Epi doses data different from standard doses (ped: 0.01mg/kg, adult: 0.3-0.5mg) |
| 3. | Symptoms of diarrhea |
| 4. | ATCD allergy to a different agent than the one in question |
| 5. | Secondary anaphylactic reaction to iodine |
| 6. | Secondary anaphylactic reaction to a sting or bite |
| 7. | Secondary anaphylactic reaction to an unknown allergen |

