Note that the first two criteria of the rule for all the combined severity of biphasic reactions (Table 4) were, at the time of diversion, contained in a single criterion: "standard or non-standard doses of IM epinephrine." However, because this criterion contained several pieces of information, it was divided into two new criteria to simplify and clarify data collection. For the first criterion (number of doses of ER in the emergency department), not receiving repeated intramuscular doses of epinephrine decreased the likelihood of having a biphasic reaction. For the second criterion (different doses from standard doses), receiving standard intramuscular doses of epinephrine decreased the likelihood of having a biphasic reaction compared to receiving non-standard intramuscular doses of epinephrine.

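### Do the 100% sensitivity and the AUC of 0.874 belong to the seven-item Table 4 rule that Phase 2 will score?

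*Combined protocol and SAP*

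**What the plan says.** All the key text is in the Steps Taken section of the combined protocol and SAP.

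- The Phase 1 summary describes the second derived rule as covering "all biphasic reactions (100%, 7 variable sensitivity; Table 4", and adds that "Areas below the ROC curve were 0.896 and 0.874, respectively". The second AUC is therefore the Table 4 value. Predictions are said to come from a weighted linear combination of the selected variables.
- Table 4, titled "RETROSPECTIVELY DERIVED CLINICAL DECISION RULE FOR BIPHASIC REACTIONS (ALL SEVERITIES CONFUSED", lists seven items. Item 1 is "Number of doses of O.R. in the emergency room" (the translation garbles the drug name; the note shows that epinephrine is meant). Item 2 is a dose that differs from the standard.
- The note after Table 4 says that these two items "were, at the time of diversion, contained in a single criterion", labelled "standard or non-standard doses of IM epinephrine". It explains: "because this criterion contained several pieces of information, it was divided into two new criteria to simplify and clarify data collection". It then gives a direction for each part. For the first, "not receiving repeated intramuscular doses of epinephrine decreased the likelihood of having a biphasic reaction"; for the second, standard doses went with a lower likelihood than non-standard ones.

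The questionnaire in the Appendix collects the two parts as separate yes/no items. Under Data analysis, all three rules are applied to every included patient, and the best derived rule is chosen on the sensitivity obtained.

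**The concern.** A validation study tests a fixed rule. If Phase 1 fitted one term where Phase 2 has two items, the 100% and 0.874 may belong to a form of the rule that is no longer in use. The plan does not say which form they describe, mentions no refit, and gives no weights for the two items. Two groups of patients look unsettled:

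- those with both repeated and non-standard doses;
- those with one dose before arrival and one in the emergency room, who had repeated doses overall but not in the emergency room.

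At stake is whether Phase 2 can say that this rule kept its sensitivity. Yearly interim analyses are planned, so there is also a worry that the coding could be settled after outcomes are known.

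**Working it through.** **The stated figures.** The 100% and 0.874 cannot be recomputed. The document gives no Phase 1 sample size, event count, coefficients, intercept or cut-off. The check is therefore on the counts and the text.

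**Counting.** Table 4 has 7 items. Merging items 1 and 2 gives 7 - 2 + 1 = 6 criteria, with 5 items outside the merged one. A categorical criterion with L levels, all entered, adds L - 1 terms to a regression.

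| Form of the original criterion | Model terms | Matches 7? |
|---|---|---|
| 2 levels | 5 + 1 = 6 | no |
| 3 levels | 5 + 2 = 7 | yes |
| 4 levels | 5 + 3 = 8 | no |
| Split form refitted, two yes/no items | 5 + 2 = 7 | yes |

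Two of the four readings give the stated count. The three-level reading fits the rest of the text. The note says the single criterion held several pieces of information and reports two effects, which is what a three-level factor yields. Table 4 also lists iodine, sting or bite, and unknown allergen as separate items, which suggests counting by term. On that reading the two yes/no items are the two indicator terms already in the model, and the Phase 1 weights carry over for every patient with at most one of them.

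**Patients with both items.** Two yes/no answers give 2 x 2 = 4 combinations, one more than three levels. In a linear combination of seven separate items, a patient with both simply receives both weights. If the original levels were mutually exclusive, any such Phase 1 patient had to be assigned to one of them, so the Phase 1 coding either settles the matter or never met the case.

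**Setting of the doses.** Write (doses before arrival, doses in the emergency room) and read repeated as more than one. Then (0,2) and (1,2) are repeated on either count, while (1,1), (2,0) and (2,1) are repeated overall only. Table 4 item 1 names the emergency room, and the note repeats that setting when describing this item. Table 3 has a separate pre-arrival item and Table 4 has none. Read plainly, pre-arrival doses do not count towards the Phase 2 item. The questionnaire also has arrival time, separate pre-arrival and total-dose items, and up to six timed dose entries. If those entries are epinephrine (the drug name there is garbled), either count can be rebuilt.

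**Use of the 100% figure.** The sample size rests on sensitivity 98%, precision 5%, prevalence 6% and 95% confidence: 1.96² x 0.98 x 0.02 / (0.05² x 0.06) = 501.97, rounded up to 502. Adding 10% gives 502 x 1.10 = 552.2, so 553, as stated. Neither the 100% nor the number of variables enters.

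**Scale.** Expected cases are 553 x 0.06 = 33.2, or 502 x 0.06 = 30.1 without the missing-data allowance. One reclassified case moves sensitivity by 1/33.2 = 3.0 or 1/30.1 = 3.3 percentage points. How many cases would cross the cut-off, if any, cannot be derived.

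**The case for a change.** The strongest case for a change is that a weighted score has to be fully specified before it is validated. Splitting one term needs either two weights or a rule for recombining the answers, and the note supplies only directions. The three-level reading is an inference. Phase 2 exists to see whether sensitivity is maintained, so its score should be the one behind the Phase 1 figure. Two reclassified cases would move the estimate by about 6 points, more than the planned 5% precision. Clarification would take only a few sentences.

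Part of this stands. A reader cannot reproduce the Table 4 score from the document, and the text does not say which form produced the 100%. But the missing coefficients and cut-off affect both derived rules and do not arise from this split. The choice between rules uses the sensitivity obtained in Phase 2, which needs one fixed scoring and not identity with the Phase 1 form; under Potential Outcomes, ease of use decides if more than one rule is effective. No formal test against 100% is planned. The two-case example is hypothetical. The worry about coding after the event assumes departure from a coding that the fitted Phase 1 model already fixes, and nothing in the plan proposes that.

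**Conclusion.** No change to the plan follows. The ambiguity is real but small: the text leaves open whether 100% and 0.874 describe the unsplit or the split form, and how the two answers map to the Phase 1 weights. It does not amount to a contradiction, because a three-level criterion counted by term gives exactly seven. The plan states no wrong scoring rule, and no figure is shown to be wrong. The effect on sensitivity could be nil and is not computable from the document; it concerns one of three rules and leaves the 553 patients unaffected. The conclusion assumes that the investigators still hold the Phase 1 coding and will score Table 4 by it, or by a Phase 1 refit if one was made. That is the ordinary way an analyst would fill this gap, and the Phase 2 questionnaire collects both components.

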1. GOALS AND ASSUMPTIONS

The main objective of Phase 2 of our study is to validate prospectively and on a theoretical basis the rules of clinical decisions from previous phases of our research project. This will allow us to assess the internal validity of the different rules derived in the same three circles (Chicoutimi, Jonquière, Alma). In addition, the evaluation of the results will identify the most effective rule.

The hypothesis of this study is that one of the derived rules will, when applied to a cohort of patients prospectively, adequately identify (sensitivity maintained) patients at low risk of biphasic reaction following an anaphylactic reaction.

If the results of the Phase 2 study are successful, a phase 3 will be put forward. The objective of this third phase will be to apply the most effective rule in real time to patients who have undergone an anaphylactic reaction in different hospitals of the RIUSSS of the University of Sherbrooke, i.e. to complete the validation of the rule in a different population.

In the event of an inconclusive Phase 2 result for the three rules under study, the investigators propose to group the data from Phases 1 and 2 to attempt a final diversion of a new clinical decision rule. If this ultimate diversion is quite different from the previously tested rules and is clinically plausible, a new validation attempt will be made (details below).

1. METHODOLOGICAL

Based on the three rules of clinical decision (2 derivatives and one based on the literature review), a prospective observational study will be carried out in the emergency departments of Chicoutimi, Jonquière and Alma. Data collection for this theoretical validation phase has been underway since December 2019, having received the approval of the various local research committees (ethics, scientific and convenience).

Inclusion and exclusion criteria

The inclusion criteria will be: all patients of minor or adult age who have had anaphylaxis that meet the known diagnostic criteria. In addition, if a patient presents with confirmed exposure to an allergen and symptoms that do not yet meet the anaphylaxis criteria, they may be included in the study. This will only be possible if the doctor deems that he will inevitably progress to anaphylaxis and treat him in this way. Those who have had a reaction to taking a drug (e.g. IECA), who are known for a hereditary pathology (hereditary angioedema), immune OR other pathology giving an anaphylactoid reaction will be excluded, as in Phase 1 of the study.

Sample size

The required sample size was adjusted for the primary objective based primarily on the study of sensitivity and specificity. As a low prevalence of biphasic reactions is expected, a calculation based on specificity is useless, therefore to be rejected. Thus, using the statistician involved in the study and using a sample size calculation adapted for a confidence interval on a ratio adjusted according to the Buderer¹³ formula, it was determined that it was necessary to have 553 patients in total to estimate a sensitivity of at least 98% with a confidence level of 95% according to an accuracy of 5% and an expected prevalence of 6%. Note that a 10% rate was added to the initial size calculation to manage the possibility of missing data. The prevalence of 6% was determined from the prevalence of biphasic reactions observed when collecting Phase 1 data from the same study..

Data collection

In the face of a case of anaphylaxis, the doctor will have to answer a short questionnaire developed with the variables present in each of the three rules (questionnaire available in appendix). The variables were randomly arranged on the questionnaire so that no rules could be recognized or inferred. If the doctor deems that a patient who does not yet present the anaphylaxis criteria, but in the absence of ahead, will eventually progress to real anaphylaxis, he or she will have to indicate it at the appropriate location on the questionnaire. Indeed, as mentioned above, these patients will be included in the study, but we will independently analyze the results of this sample to determine if they are different from the overall results in subgroup analyses.

The questionnaire will be available at several key locations, including in the paper-based resuscitation rooms in the three emergencies where data collection will take place. The questionnaire will also be systematically placed on the file of patients with suspected anaphylaxis at triage. The doctor will be required to complete the questionnaire anonymously, but will be required to provide the patient's file number. This will be done after the initial stabilization. After completing the questionnaire, the physician will simply be able to continue to care for the patient as he would have done in accord with his standard clinical practice. No decision rules will be applied to patients. The answers provided to

the questionnaire will therefore have no impact on the clinical decisions made by the treating physician. The research team will then review each of these files to assess whether or not there was a biphasic reaction and whether it was clinically significant (according to the NIAID/FAAN²criteria).

At the next emergency department meetings involved, doctors will be notified of the operation of the current study. Recalls will be made as required during the course of the study to ensure the involvement of the medical profession. Administrative officers and triage nurses will also be advised to add the questionnaire to all potential anaphylaxis files.

Data analysis

Based on the data, all three rules will be theoretically applied to all included patients. This will determine which patients would have been dismissed or observed and under what rule. Subsequently, the records of these same patients will be retrospectively analyzed to determine the occurrence of biphasic reaction after the initial visit. It will be particularly interesting to assess whether the biphasic reaction occurred during the emergency observation period.

As we seek to evaluate the effectiveness of diagnostic rules, statistical analyses will focus primarily on a study of sensitivity and specificity. In order to be able to properly characterize the different derived rules, it will also be relevant to obtain the predicted positive and negative values. Confidence intervals will be built around the proportions obtained. The choice of the best derived rule will be based on the sensitivity value obtained. Indeed, we seek to maximize this parameter in order to obtain the combination of variables that will allow us to use a rule to safely discharge patients with low risk of biphasic reaction. In the event that none of the rules maintain a fairly high sensitivity and/or negative predictive value, all Phase 1 and Phase 2 data will be jointly analyzed and a re-derivation test of a statistically stronger rule will be conducted, again using logistic regression models.

Considering that the sample size has been revised, the study schedule has also been revised. It is therefore more realistic for us to expect a period of at least 2 to 3 years to complete the data collection for this phase 2. However, we propose to do an interim analysis of the results at least once a year. Data collection is currently planned for 2020 and 2021 with an initial interim analysis in May 2020. The team is ready to extend the "recruitment" period as needed to reach the 553 patients needed. Data collection is currently well underway and the goal of recruiting 200 to 250 patients per year seems realistic.

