1. POTENTIAL OUTCOMES

If one of the clinical decision rules is sufficiently effective during this phase of the study (phase 2), i.e. maintaining good sensitivity and negative predictive value, it can be applied in real time. If more than one rule is effective, the most easily applicable rule will be chosen. This will be done as part of a phase 3 study with systematic follow-up for each patient for whom the rule has been applied.

If Phase 3 proves it is conclusive, the rule demonstrates a strong negative predictive value during its actual clinical use and good external validity, and it will be disseminated on a larger scale. Thus, we hope to facilitate the management of anaphylaxis in the emergency room by allowing **the early and safe release** of many patients who have been treated for an anaphylactic reaction, ensuring that the risks of biphasic reactions are minimized.

The rule bearing the name of the geographic region from which it originates could help to spread the environment of the CIUSSS SLSJ. In addition, having received financial assistance and support from the MF/MU department of the University of Sherbrooke, the investigators will ensure that the name of the University and the Department they represent is clearly visible in their publication; also helping to spread the way of this institution.

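### The figure of 553 is arithmetically right, but about 30 expected events do not support the stated 5-point accuracy for sensitivity (exact half-width 5.8 points with no miss, 8.6 with one), and no interval method is named

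*Combined protocol and SAP*

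**What the plan says.** The Sample size paragraph under Methodological bases the calculation on sensitivity, uses the Buderer formula, and requires "553 patients in total to estimate a sensitivity of at least 98% with a confidence level of 95% according to an accuracy of 5" per cent. The expected prevalence is 6%, and 10% is added for missing data. On the source of the prevalence it says: "The prevalence of 6% was determined from the prevalence of biphasic reactions observed when collecting Phase 1 data from the same study". The number of biphasic reactions that this implies is not given.

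The Data analysis paragraph says "Confidence intervals will be built around the proportions obtained" without naming a method. It then says "The choice of the best derived rule will be based on the sensitivity value obtained".

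Steps taken describes the two Phase 1 rules: "The first rule assesses the probability of clinically significant biphasic reactions (sensitivity of 90%, 7 variables; Table 3) and the second, all biphasic reactions", the second with a Phase 1 sensitivity of 100%.

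**The concern.** The 5% is the plan's only statement of precision. Someone who sees 98% with 5 points of accuracy will expect a result near 98% to exclude sensitivities below about 93%. The effective sample for sensitivity, however, is the patients who have a biphasic reaction, not the 553. At 6% prevalence that is about 30 people, and a rule with 98% sensitivity would be expected to miss fewer than one of them. A normal approximation is least trustworthy in that setting.

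Sensitivity is also what the rules are ranked on, and one event in 30 is worth 3.3 points (1/30). For a rule meant to send patients home early, the lower limit of sensitivity matters most. If the interval method stays open until the data are in, the lower limit reported for one and the same result can differ widely.

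**Working it through.** **Inputs (Sample size paragraph).** Sensitivity 0.98; half-width d = 0.05; 95% confidence, z = 1.96; prevalence 0.06; 10% added. The plan does not say whether the interval is two-sided; two-sided is assumed because it reproduces 553.

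**Step 1: the plan's figure.**
- n = z² × Se × (1 − Se) / (d² × prevalence) = 1.96² × 0.98 × 0.02 / (0.05² × 0.06) = 501.97, rounded up to 502.
- 502 × 1.10 = 552.2, rounded up to 553. The figure reproduces.

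**Step 2: the events behind it.**
- 502 × 0.06 = 30.1 events, or 553 × 0.06 = 33.2 if no data are missing.
- Expected misses: 30.1 × 0.02 = 0.60.
- With 30 events at a true 98%: P(no miss) = 0.98³⁰ = 0.545; P(one miss) = 30 × 0.02 × 0.98²⁹ = 0.334.

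**Step 3: the normal approximation at those results.** Its half-width is 0 at 30/30 and 1.96 × √[(29/30)(1/30)/30] = 6.4 points at 29/30. Its actual coverage with 30 events at a true 98% is 45%, mainly because the zero-width interval at 30/30, which occurs 54.5% of the time, cannot contain 98%.

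**Step 4: other 95% intervals with 30 events.** Limits in %, half-width in points in brackets. The average is taken over the binomial distribution of misses at a true 98%.

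| Method | 30/30 | 29/30 | Average half-width, 30 events | Average half-width, 33 events |
|---|---|---|---|---|
| Clopper-Pearson (exact) | 88.4 to 100 (5.8) | 82.8 to 99.9 (8.6) | 7.3 | 6.8 |
| Wilson | 88.7 to 100 (5.7) | 83.3 to 99.4 (8.0) | 7.0 | 6.5 |
| Jeffreys, upper limit set to 100 at 30/30 | 92.0 to 100 (4.0) | 85.5 to 99.6 (7.1) | 5.7 | 5.3 |
| Likelihood ratio | 93.8 to 100 (3.1) | 86.1 to 99.8 (6.8) | 5.1 | 4.8 |

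With 33 events the exact half-width is 5.3 points with no miss (lower limit 89.4%) and 7.8 with one (lower limit 84.2%).

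**Step 5: let the event count vary.** With events drawn from Binomial(502, 0.06), the central 95% range is 20 to 41.

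| Method | Average half-width | P(half-width ≤ 5 points) | Events for an average of 5 points |
|---|---|---|---|
| Clopper-Pearson | 7.5 | 7% | 52 |
| Wilson | 7.1 | 9% | 49 |
| Jeffreys | 5.8 | 48% | 37 |
| Likelihood ratio | 5.2 | 55% | 32 |

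**Step 6: distance from the estimate to the lower limit.** The plan did not state its 5% on this measure, but it is the one that bears on early discharge. The exact lower limit lies 11.6 points below the estimate at 30/30 and 13.9 below at 29/30. For Jeffreys and likelihood ratio the distance is 6 to 8 points with no miss and 10 to 11 with one.

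**Step 7: the Table 3 rule (secondary).** Its Phase 1 sensitivity is 90%, and its outcome is narrower than the reactions behind the 6%. Even if all 30 events counted, the planning formula gives 1.96 × √(0.9 × 0.1/30) = 10.7 points, and 27/30 gives an exact interval of 73.5% to 97.9% (half-width 12.2). The prevalence of clinically significant reactions is not in the documents, so 30 is an upper assumption here.

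**The case against.** The strongest reply is that the shortfall depends on the interval method. The exact interval is the widest of the four in Step 4. At 30/30, the single most likely result, Jeffreys and likelihood ratio are inside 5 points, and likelihood ratio averages 4.8 if all 33 events are available. At 30 events and a true 98%, all four methods have the same coverage, 97.8%, so coverage at that point rules out the normal approximation without favouring Wilson or Clopper-Pearson over the two narrower methods. The 5% can also be read as a planning input rather than a promise for each realised count: 98% of 30 is 29.4, a result that cannot occur. Finally, the rules are ranked on a point estimate, no threshold uses the 5%, no rule is applied to patients in Phase 2, and for the next step the plan says "This will be done as part of a phase 3 study with systematic follow-up for each patient for whom the rule has been applied".

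Much of this stands, and it limits the consequences. It does not rescue the statement. Under the two most favourable methods the half-width still exceeds 5 points about half the time (52% and 45%), and under exact and Wilson more than 90% of the time. That the answer turns on the method is itself the reason to name one in advance. The Table 3 point is separate, and the conclusion does not rest on it.

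**Conclusion.** The concern holds and should be fixed. The sample size is not an arithmetic error; the precision attached to it is not a property of the design. At 30 events and a true sensitivity of 98%, the average half-width is above 5 points under all four methods, from 5.1 (likelihood ratio) to 7.3 (exact). Only likelihood ratio with no missing data averages below 5. Even a perfect 30/30 leaves an exact lower limit of 88.4%.

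This assumes two-sided 95% intervals, the plan's own 98% and 6%, and that missing data use up the 10% allowance; the 33-event figures show the effect of relaxing the last assumption. It poses no direct risk to patients in Phase 2. What is at stake is how much confidence is placed in a rule carried forward to Phase 3.

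**What to change.** Keep 553. In the Sample size paragraph, replace the 5% accuracy statement with wording such as:

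> About 30 biphasic reactions are expected (33 if no data are missing). With 30, the exact 95% interval for sensitivity is 88.4% to 100% if none is missed and 82.8% to 99.9% if one is missed.

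In the Data analysis paragraph, name Wilson or Clopper-Pearson as the method for sensitivity and negative predictive value, and exclude the normal approximation, which would report a perfect result with zero width. Jeffreys or likelihood ratio would also avoid that; what matters most is that the method is fixed before the data are analysed.

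As a secondary addition, give the expected precision for clinically significant reactions and the Table 3 rule separately, using that outcome's Phase 1 prevalence, which the investigators should have.

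The cost is wording only, with no additional patients. The one drawback is that the stated precision becomes less favourable.

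### Patients not yet meeting the anaphylaxis criteria are checked only against a total that contains them, and no estimate is planned for patients who do meet the criteria

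*Combined protocol and SAP*

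**What the plan says.** Under Inclusion and exclusion criteria (Methodological section), a patient with confirmed allergen exposure and "symptoms that do not yet meet the anaphylaxis criteria, they may be included in the study". A condition follows: "This will only be possible if the doctor deems that he will inevitably progress to anaphylaxis and treat him in this way". The questionnaire in the appendix has a yes/no item for meeting the criteria and a follow-up item for this route of entry, so the group can be identified.

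Under Data analysis, "all three rules will be theoretically applied to all included patients". These patients are therefore part of the main estimate. Sensitivity is the deciding parameter: "The choice of the best derived rule will be based on the sensitivity value obtained". On precision, the text says "Confidence intervals will be built around the proportions obtained", without naming the type of interval.

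The one provision specific to this group is under Data collection: "we will independently analyze the results of this sample to determine if they are different from the overall results in subgroup analyses". No test, margin or threshold for a difference is given, and no analysis restricted to criteria-met patients is stated anywhere.

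The hypothesis in Goals and Assumptions is about identifying "patients at low risk of biphasic reaction following an anaphylactic reaction". The same section describes Phase 3 as applying the chosen rule to patients who have had such a reaction.

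**The concern.** The comparison sets a part against a whole that includes it. The two estimates are not independent, and the contrast understates how far the subgroup differs from everyone else.

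The contrast also does not address the question that matters for the hypothesis: what is each rule's sensitivity in patients who meet the criteria? That is the population in which Phase 1 derived its two rules and in which Phase 3 would use the winner. The all-included estimate covers a wider population, and the plan does not commit to showing the narrower one beside it. Because rules are ranked on sensitivity with few events, a shift of even a few points could matter to the ranking. If the criteria-met figures are produced only after the results are known, choosing which set to present becomes a post hoc decision. At least yearly interim analyses add to that risk.

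**Working it through.** **Inputs from the protocol (Sample size).** Sensitivity 0.98, precision 0.05, 95% confidence, prevalence 0.06, 10% added for missing data, total 553.

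**Reproducing the plan's figure.** Buderer: n = 1.96² × 0.98 × 0.02 / (0.05² × 0.06) = 501.95 (with the unrounded normal quantile), rounded up to 502. Then 502 × 1.10 = 552.2, rounded up to 553. The stated total reproduces, and this point does not affect it. Expected biphasic reactions among 502 evaluable patients: 502 × 0.06 ≈ 30.

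**Algebra.** Let f be the subgroup's share of all biphasic reactions, S its sensitivity, and R the sensitivity in the remaining (criteria-met) patients. The all-included sensitivity is O = fS + (1 − f)R. Hence:
- planned contrast: S − O = (1 − f)(S − R)
- shift in the main estimate: O − R = f(S − R)

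**Assumptions.** The documents give no subgroup size, so f is taken as 5% to 30%, with 6% prevalence in both groups so that the share of patients equals the share of reactions. The true difference S − R is set at 10 points in either direction.

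| Assumed share f | Subgroup reactions (30.12 × f) | Planned contrast, 10 × (1 − f) | Shift in main estimate, 10 × f | Criteria-met reactions kept |
|---|---|---|---|---|
| 5% | 1.5 | 9.5 points | 0.5 points | 28.6 |
| 10% | 3.0 | 9 points | 1 point | 27.1 |
| 20% | 6.0 | 8 points | 2 points | 24.1 |
| 30% | 9.0 | 7 points | 3 points | 21.1 |

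**Precision within the subgroup.** Even if a rule detected every reaction, the exact (Clopper-Pearson) 95% lower limit would be 16% for 2/2, 29% for 3/3, 54% for 6/6 and 66% for 9/9.

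**What the comparator costs if a test were used.** The plan names none, so this is only an illustration. Assume sensitivity 0.98 in criteria-met patients and 0.80 in the subgroup (an 18-point gap), 30 reactions in all, and Fisher's exact test at 5%, with the total treated as if it were an independent group. Enumerating all outcomes gives the probability of flagging the gap:

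| Subgroup reactions | Against the total | Against the remaining patients |
|---|---|---|
| 3 of 30 | 6% | 10% |
| 6 of 30 | 7% | 25% |
| 9 of 30 | 1% | 20% |

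The comparison with the remaining patients does better, but neither detects the gap reliably. With 3 reactions, the subgroup would show a perfect 3/3 with probability 0.80³ = 51%.

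**Recovering the criteria-met result.** With counts in hand it follows by subtraction: overall 29/30 (96.7%) and subgroup 2/3 leave 27/27 (100%).

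**The case against.** A reader might infer that the planned check cannot show whether these patients distort the main estimate, or that it will almost always find no difference. The documents support neither. The planned contrast is zero only when the true contrast is zero; it is attenuated, not erased. The criteria-met result can be recovered by subtraction. With no test, threshold or subgroup size stated, no rate of finding a difference can be derived. Nor does any passage make pooling conditional on this check.

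A second tempting reading is that a first progression to anaphylaxis in these patients would be counted as a biphasic reaction. The Problem section largely answers it: a biphasic reaction requires prior resolution of the initial reaction, which uninterrupted progression does not satisfy.

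The defence has further force. Inclusion was deliberate, restricted and disclosed, and the group is flagged and examined separately. The text appears to be a translation, so the wording about overall results may mean no more than separate reporting. The shift of 0.5 to 3 points is smaller than the planned 5-point precision. Few events, not the comparator alone, limit any subgroup comparison, including one against the remaining patients.

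All of this limits the size of the point. It does not remove two facts: the stated comparator contains the subgroup, and no criteria-met estimate is promised. That subtraction is possible does not mean that the plan commits to it.

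**Conclusion.** The point holds as a cheap improvement. The plan's only check on patients not yet meeting the criteria uses a comparator that shrinks a true difference by (1 − f), and it omits the estimate for the population named in the hypothesis. For assumed shares of 5% to 30%, a true 10-point difference would appear as 9.5 to 7 points, and the all-included sensitivity would differ from the criteria-met value by 0.5 to 3 points. These figures rest on the assumed shares, equal 6% prevalence in both groups, 502 evaluable patients and the chosen 10-point difference; the documents fix neither the share nor the difference. The main analysis is not shown to be distorted, and the sample size stands.

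**What to change.** Add to Data analysis: sensitivity, specificity and both predictive values, with confidence intervals, will be reported for all three rules in patients who met the anaphylaxis criteria, beside the all-included result. State that any contrast for patients not yet meeting the criteria is descriptive and made against the remaining patients, not the total.

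The cost is one sentence and one table. The questionnaire item already identifies the patients, so no new data and no larger sample are needed. The criteria-met intervals will be somewhat wider, because about 21 to 29 of the 30 expected reactions are kept under the assumed shares. For a rule that detects every reaction, the exact 95% lower limit would be 84% for 21/21 or 88% for 29/29, against 88% for 30/30.
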